## 1 Protocol Outline

Title	Use, safety and tolerability of intravenous epoprostenol (Veletri®) in patients with severe pulmonary arterial hypertension
Short title:	TIVOLI
Local Project ID	9713228
Phase:	Observational study / “Anwendungsbeobachtung” according to § 67 subsection 6 German Medicinal Products Act (AMG)
Principal / Coordinating Investigator	[name]. med. [name] Thoraxclinic at Heidelberg University Hospital 1. Centre for pulmonary hypertension [name] [name]
Financing	Co-financing by pharmaceutical industry: Actelion Pharmaceuticals
Indication	ICD-10 I27.0 Primary pulmonary hypertension  MedDRA (V. 12.0) Pulmonary Hypertension 10037400, Level 4
Trial Population	Inclusion Criteria 
 
1. male or female patients with pulmonary arterial hypertension (PAH)
 
2. adult patients having completed his/her 18th birthday
 
3. patients in need of treatment escalation with i.v. epoprostenol according to current guidelines
 
4. (PAH) confirmed by right heart catheter (RHC) before enrolment, i.e. mPAP <math>\geq</math>25 mmHg at rest, PAWP <math>\leq</math>15 mmHg
 
5. able to understand and willing to sign the Informed Consent Form
 
 Exclusion Criteria 
 
1. known intolerance to epoprostenol or one of its excipients
 
2. participation in any clinical drug trial within 4 weeks prior to screening of this study and/or patient, who is scheduled to
 

	
receive an investigational medicinal product (IMP) during the course of this study
 
pregnancy or lactation


Objectives / Endpoints
	
Primary [Objectives / Endpoints]
 
 
- To collect and explore real-life data on the use, safety and tolerability of a systematic drug management of intravenous epoprostenol (Veletri®) treatment in patients with PAH.
 
 
Real-life safety and tolerability data will be obtained by listings of the frequency of i.v. epoprostenol (Veletri®)-associated adverse drug reactions (ADRs), serious adverse events (SAEs) during i.v. epoprostenol therapy and AEs during i.v. epoprostenol therapy.
 
Secondary [Objectives / Endpoints]
 
To assess the real world clinical effectiveness of i.v. epoprostenol (Veletri®) therapy by collection of the following data (according to clinical practice):
 
 
- demography
 
- vital signs
 
- exercise capacity as measured by six minute walking distance
 
- N-terminal pro-brain natriuretic peptide (NTproBNP)
 
- World Health Organization (WHO) functional class
 
- Borg dyspnea score
 
- blood gas analysis
 
- right heart size and function (presence/absence of pericardial effusion and tricuspid annular plane systolic excursion (TAPSE), right atrial and ventricular area, systolic pulmonary arterial pressure, right ventricular pump function, assessed by echocardiography)
 
- haemodynamics (right arterial pressure (RAP); mean pulmonary arterial pressure (mPAP); cardiac output (CO), cardiac index (CI); pulmonary vascular resistance (PVR); PVR index (PVRI); pulmonary capillary wedge pressure (PCWP) assessed by right heart catheterisation and tricuspid regurgitant jet velocity (TRJV) assessed by echocardiography)
 
- symptoms of PAH
 
- outcome (survival, transplant-free survival)
 

Trial Design	
This is a non-interventional, observational and prospective, multicenter study to evaluate the use, safety and tolerability of i.v. epoprostenol therapy (Veletri®) in routine practice according to the German Drug Law (AMG, §67(6)).
 
Patients with invasively diagnosed PAH receiving targeted PAH combination treatment in need of treatment escalation with i.v. epoprostenol, according to medically indicated decision on treatment-escalation, will be included in this non-interventional, observational study. This study is performed as a non-interventional trial using a prospective, open label, multicenter clinical study design with treatment according to current medical practice.
 
Patients will be assessed according to routine clinical examinations in their respective pulmonary hypertension expert center. According to the current guidelines, patients will be seen in the expert center about every three months. This will allow to collect data within the first 6 months of treatment and compare changes between baseline, 3 and 6 months (~24 weeks).
 
Routine medical examinations comprise of medical history, physical examination, electrocardiogram (ECG), laboratory testing (including NT-proBNP), echocardiography at rest, and right heart catheterization according to clinical practice of the PH center. If patients fulfill the inclusion criteria they will be invited to join the study. The prospective period of data collection will comprise of a ~24-week study period a follow-up phase of about 30±7 days.
 
Outcome (survival and transplant-free survival) of all patients will be assessed when the last patient has terminated his/her ~24 week observation period.

Medicinal product under observation	
Epoprostenol i.v. (Veletri®) will be applied according to general practice. Dosage will be individually up-titrated according to the physician's and the patient's estimation.

Sample Size	
In this open label, multicentre study patients with PAH will receive i.v. epoprostenol according to current clinical practice. Patients in need of treatment escalation according to the current guidelines receive at least

	
dual combination treatment with two PAH-targeted drugs and have an unsatisfying long-term clinical response or are still in an intermediate or high risk group.
 
The main analyses will be the description of use, safety data and the change of clinical data by i.v. epoprostenol during the course of the study.
 
A sample of ~15 patients will be included into the observational study to gain insights into and collect data regarding the use, safety and tolerability of a systematic drug management of i.v. epoprostenol treatment (Veletri®).

Statistical Analysis	
General
 
Descriptive statistics:
 
 
- All data (demographic and other baseline characteristics, continuous data at each visit and their change to baseline) will be listed and trial summary tables will be provided. The data from all centers will be pooled.
 
- Descriptive statistics will be displayed (arithmetic mean, median, standard deviation, standard error, 95% confidence limits of mean and median, first and third quartiles, minimum, and maximum for quantitative variables). Frequency tables for qualitative data will be provided.
 

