#### **3.2 Secondary Objectives and Endpoints**

2) To assess the real world clinical effectiveness of epoprostenol (Veletri®) therapy by collection of the following data (according to clinical practice), if available:

- demography
- vital signs
- exercise capacity as measured by six minute walking distance
- N-terminal pro-brain natriuretic peptide (NTproBNP)
- World Health Organization (WHO) functional class
- Borg dyspnea score
- blood gas analysis
- right heart size and function (presence/absence of pericardial effusion and tricuspid annular plane systolic excursion (TAPSE), right atrial and ventricular area, systolic pulmonary arterial pressure, right ventricular pump function, assessed by echocardiography)
- haemodynamics (right arterial pressure (RAP); mean pulmonary arterial pressure (mPAP); cardiac output (CO), cardiac index (CI); pulmonary vascular resistance (PVR); PVR index (PVRI); pulmonary capillary wedge pressure (PCWP) assessed by right heart catheterisation and tricuspid regurgitant jet velocity (TRJV) assessed by echocardiography)

- symptoms of PAH
- outcome (survival, transplant-free survival)

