##### **4.1 Study population**

In this open label, multicenter non-interventional, observational study patients with PAH will receive medically indicated i.v. epoprostenol (Veletri®) according to a systematic drug management including initiation, administration, storage, handling of the infusion system and patient education. Patients in need of treatment escalation according to the current guidelines receiving at least dual oral combination treatment with two PAH-targeted drugs and having an unsatisfying long-term clinical response or are still in an intermediate or high risk group will be eligible for the study.

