### 6.3 Inclusion Criteria

1. male or female patients with pulmonary arterial hypertension (PAH)
2. adult patients having completed his/her 18th birthday

3. patients in need of treatment escalation with i.v. epoprostenol according to current guidelines
4. (PAH) confirmed by right heart catheter (RHC) before enrolment, i.e. mPAP  $\geq$ 25 mmHg at rest, PAWP  $\leq$ 15 mmHg
5. able to understand and willing to sign the Informed Consent Form.

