## **8 Data Sources**

### **8.1 Variables**

Information will be collected as available and per clinical practice visit schedule. Data will be entered by the investigator / member of the study team into a standardized CRF.

Data will be collected for each patient at initiation of i.v. epoprostenol (Veletri®) and throughout the observational period from the existing medical record at any clinical visit on the respective CRF. If a patient's data collection is terminated, the date and reason for termination of data collection must be recorded on the CRF. Table 1 provides an overview of the variables collected at initiation of i.v. epoprostenol (Veletri®) and/or during the observation period (follow-up visits), if available, per clinical practice.

At initiation of a new i.v. epoprostenol (Veletri®) therapy, the data available at initiation of i.v. epoprostenol (Veletri®) will be collected for assessments stated above (points 8.1.1-8.1.10). Descriptions of clinical practice assessments are explicitly not used to alter or regulate clinical assessments in the participating centres.

According to the current guidelines, patients are likely to be seen in the expert center about every three months. This will allow to collect data within the first 6 months of treatment and compare changes between baseline, 3 and 6 months (~24 weeks).

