**Table 1: CRF data collection (as available per clinical practice from the existing medical record)**

Variable / Clinical characteristics	Initiation of i.v. epoprostenol (Veletri®) therapy	Follow-up (at any clinical practice visit)
Informed consent	X	
Medical History	X	
Inclusion/Exclusion Criteria Review	X	
Demographics (age, gender, country)	X	
Physical examination and vital signs	X	X
WHO classification	X	X
Electrocardiogram - ECG	X	X
Echocardiography at rest	X	X
Right heart catheterization	X	X
6MWD-test	X	X
(Lung function test	X	X
Patient Questionnaire 1 (QoL)	X	X
Patient Questionnaire 2 (Borg dispnoe score)	X	X
Lab tests/assay 1 (including NT-proBNP)	X	X
Lab tests/assay 2 (Pregnancy test)	X	

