## 10 Statistical Procedures

### 10.1 Sample Size Calculation

A sample of ~15 patients will be included into the observational study to gain insights into and collect data regarding the use, safety and tolerability of a systematic drug management of i.v. epoprostenol treatment (Veletri®).

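### Before-after change in patients selected for poor status is tested and presented as clinical effectiveness, although the design cannot attribute that change to epoprostenol in either direction

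*Protocol*

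**What the plan says.** **Who enters.** Protocol section 6.3 requires "patients in need of treatment escalation with i.v. epoprostenol according to current guidelines". Section 4.1 adds that patients on at least dual oral combination treatment "having an unsatisfying long-term clinical response or are still in an intermediate or high risk group will be eligible for the study". The Sample Size row of the outline (section 1) says much the same: "have an unsatisfying long-term clinical response or are still in an intermediate or high risk group".

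**What they are compared with.** Section 8.1 sets the starting point: "the data available at initiation of i.v. epoprostenol (Veletri®) will be collected for assessments stated above (points 8.1.1-8.1.10"). Table 1 in section 8.2 has one column for initiation and one headed "Follow-up (at any clinical practice visit"). It lists medical history, but no earlier 6MWD, NT-proBNP, functional class, echocardiography or catheter values. There is one cohort. Section 10.1 gives its size without a calculation: "A sample of ~15 patients will be included into the observational study to gain insights into and collect data".

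**What is done with the change.** Section 10.4.1 calls for formal significance tests of the secondary efficacy variables, baseline against 3 months and baseline against 6 months, under a general two-sided error rate of 0.05. It also plans a Wilcoxon test of the change in WHO functional class.

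**How the change is presented.** The secondary objective in section 3.2 is "To assess the real world clinical effectiveness of epoprostenol (Veletri®) therapy by collection of the following data (according to clinical practice), if available", and the outline carries the same objective. The outline also places clinical change among the main analyses: "The main analyses will be the description of use, safety data and the change of clinical data by i.v. epoprostenol during the course of the" … No section warns that the change may not be due to the drug.

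**The concern.** A cohort chosen because it is doing badly, and then compared only with its own value at the time of choice, can change for at least three reasons: the drug, regression towards usual values, and the underlying course of the disease. With one pre-treatment time point and no comparator, the data cannot divide the observed change among them.

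This matters because the protocol goes beyond description. It names effectiveness as an objective, attributes change to the drug with the word *by*, and attaches significance tests that invite a yes-or-no reading. A favourable p-value could be reported as evidence of benefit when part or all of the change comes from selection. Conversely, if patients were declining before initiation, stabilisation would be real benefit that appears as no change. What is at stake is the secondary effectiveness conclusion. The use, safety and tolerability objective does not depend on it.

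**Working it through.** The protocol gives no effect size, SD, correlation or power, so there is no figure of its own to reproduce. The calculation below only illustrates how large the problem could be.

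**Inputs from the protocol:** n of about 15 (section 10.1); two-sided 0.05 and before-after tests (section 10.4.1); entry on poor status (sections 4.1 and 6.3).

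**Assumed inputs, not in the documents:** 6MWD SD 100 m; correlation between visits (rho) 0.7 to 0.9; normal values; no drug effect; paired t test; patients drawn from the lower half or the lowest third.

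**Case A: selection acts on the baseline reading itself.**
Expected rise = SD × (1 − rho) × L, where L = phi(c)/Phi(c).
- Lower half: c = 0, L = 0.3989/0.5 = 0.798.
- Lowest third: c = −0.431, L = 0.3636/0.3333 = 1.091.

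For example, the lower half with rho 0.7 gives 100 × 0.3 × 0.798 = 24 m. The rejection rates are simulated, and repeat runs agree within about one percentage point.

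| Selection | rho | Rise with no drug effect | Falsely significant improvement |
|---|---|---|---|
| Lower half | 0.7 | 24 m | about 22% |
| Lower half | 0.8 | 16 m | about 16% |
| Lower half | 0.9 | 8 m | about 10% |
| Lowest third | 0.7 | 33 m | about 37% |
| Lowest third | 0.8 | 22 m | about 25% |
| Lowest third | 0.9 | 11 m | about 15% |

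The nominal rate in the direction of improvement is 2.5%.

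**Case B: selection acts on the mean of three visits, the last being baseline.** This is closer to a long-term response.
Expected rise = SD × L × [(1 − rho)/3] / sqrt[(1 + 2 rho)/3].
- Lower half: rho 0.7 gives 100 × 0.798 × 0.1/0.894 = 9 m; rho 0.9 gives 100 × 0.798 × 0.0333/0.966 = 3 m.
- Lowest third: rho 0.7 gives 100 × 1.091 × 0.1/0.894 = 12 m; rho 0.9 gives 100 × 1.091 × 0.0333/0.966 = 4 m.

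The range is 3 to 12 m, with falsely significant improvement in about 4% to 8% of simulated trials.

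**Case C: Case A with an assumed average background decline of 10 m between baseline and follow-up.**
- rho 0.9, lower half: 8 − 10 = −2 m, false improvement about 1.6%.
- rho 0.9, lowest third: 11 − 10 = +1 m, about 2.9%.
- rho 0.7: 24 − 10 = +14 m and 33 − 10 = +23 m, so an upward bias remains.

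The same subtraction in Case B gives 3 − 10 = −7 m up to 12 − 10 = +2 m.

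The net bias therefore changes size, and even sign, with quantities that the protocol does not fix and the planned data would not reveal.

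**The case against.** The best defence has four parts.

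1. **The study is openly single-arm, non-interventional and mainly about safety, and the outline sentence speaks of description.** This stands as far as it goes: the absence of a control arm is not a defect here. It does not answer the effectiveness objective in section 3.2 or the formal tests in section 10.4.1, which go beyond description.

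2. **Entry rests on long-term response or on still being at risk, not on one bad reading.** This stands. Such wording describes persistent status and weakens regression to the mean. It is why Case B matters and why the Case A figures should be read as the upper end. No entry criterion mentions 6MWD. That response and risk are judged on the same kind of variables as the outcomes is a reasonable inference, but the protocol refers only to current guidelines.

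3. **Disease progression could work the other way.** This also stands. A reader might infer that an ineffective drug would necessarily look effective, or that false positives would always favour improvement. The documents support neither. Case C shows the bias cancelling or reversing, and even without decline a small share of significant results point to worsening.

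4. **Earlier values may not exist.** This stands in part. A reader might infer from the three-monthly visits that every patient has them. The protocol describes those visits for the treatment period and calls them likely, and newly referred patients may have no earlier values at the centre. But enrolled patients are already on combination treatment and data come from the existing record, so earlier values will often be there. The CRF itself is not shown, but Table 1 does not ask for such values.

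**Conclusion.** The point holds as a mismatch between design and claim. Patients are selected for poor status, the only comparator is their value at initiation, and the resulting change is tested and labelled effectiveness without a caveat. Drug effect, regression to the mean and disease course cannot be separated, so the effectiveness conclusion is not supported in either direction.

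The size is not established. Under the stated assumptions the spurious 6MWD change with no drug effect ranges from +33 m (selection on the baseline reading, lowest third, rho 0.7) to slightly below zero (same mechanism, lower half, rho 0.9, 10 m decline). Selection on a three-visit mean without decline gives +3 to +12 m. SD, correlation, selection fraction and decline are all assumed. It would be going too far to say that the study will overstate benefit. What can be said is that its data could not show whether it does. The primary safety and tolerability objective is untouched. The correction is cheap and changes what the study may conclude, so it should be made.

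**What to change.** **Wording.** In the outline (objectives and Sample Size row), section 3.2 and section 10.4.1, replace the effectiveness and *by* wording with: describe change from baseline during i.v. epoprostenol therapy. State once that this change cannot be attributed to the drug, because patients are selected for poor status and there is no comparator. Label the before-after tests, including the Wilcoxon test of functional class, as exploratory.

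**Data.** Add a pre-initiation column to Table 1 and the CRF. It should hold, where available in the existing record, dated values of 6MWD, Borg score, NT-proBNP, WHO class, echocardiography and right heart catheterisation from the last one or two routine visits before the escalation decision. Report each patient's pre-initiation change beside the post-initiation change. This gives context on prior course only: one or two earlier values in about 15 patients will not separate drug effect from regression or progression.

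**Cost.** Modest abstraction work for about 15 patients, and no new assessment, so the commitment in section 8.2 to add none is kept. Values will be missing for newly referred patients, and the claim becomes less favourable.

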## 2 Introduction

### 2.1 Scientific Background

Chronic pulmonary hypertension (PH) is associated with impaired exercise capacity, quality of life and right ventricular function.[1] The disease is characterized by an increase of pulmonary vascular resistance and pulmonary arterial pressure, leading to right heart insufficiency.[1, 2] Within the last decade, new disease-targeted medical therapies have been approved for treatment of pulmonary arterial hypertension (PAH).[3] Combinations of these agents have shown to further improve symptoms, 6-minute walking distance (6-MWD) and hemodynamics in PAH patients.[1, 3]

The loss of endogenous prostacyclin plays an important role in the pathogenesis of PAH. Prostacyclin has vasodilatory, anti-proliferative, anti-inflammatory and anti-thrombotic properties and is therefore an important target substance in PAH-specific therapy.[4] Epoprostenol was the first specific therapy approved for the treatment of PAH, after showing a positive effect on survival in otherwise treatment naïve patients.[5] Epoprostenol is chemically unstable with a short biological half-life of 3-5 minutes, and must be continuously administered by intravenous (i.v.) infusion using an external pump and in-dwelling central venous catheter. The application of epoprostenol is therefore aggravated by its handling, which makes it a challenge for the patient to store and administer the medication.

Flolan® was the first epoprostenol drug that was made available for treatment of pulmonary arterial hypertension. Reconstituted flolan solution is stable at 2 - 8 °C for up to 48 hours. If used immediately, reconstituted flolan is stable for up to 12 hours at room temperature (< 25 °C), or prior to use at room temperature, reconstituted flolan may be stored at 2 - 8 °C for up to 40 hours. In this case, flolan should not be infused for over 8 hours at room temperature.

With Veletri® an improved epoprostenol solution has been therefore developed to facilitate storage and administration of the drug. It provides a better stability upon reconstitution is self-preserving, does not allow the growth of micro-organisms and allows reconstitution with readily available diluents.

### 2.2 Trial Rationale/ Justification

Intravenous epoprostenol (Veletri®) is used to treat adults with certain kinds of severe pulmonary arterial hypertension (PAH) (WHO Group 1) and it has been in use worldwide for decades. It gives patients the option of up to once- weekly preparation (up to 8 cassettes at one time), and which, when prepared, stored, and used as directed, does not require ice packs. By

contract with Flolan® (epoprostenol sodium), which contains the same active pharmaceutical ingredient, it provides 24-hour room temperature stability at all concentrations.

As intravenous treatment is still complex and experience in the administration, titration and handling of i.v. application systems is rare, this non-interventional study is aimed to investigate the use of a systematically structured management of intravenous epoprostenol (Veletri®) in patients with severe pulmonary arterial hypertension within German centers according to current clinical practice.

### **3 Trial Objectives and Endpoints**

#### **3.1 Primary Objective and Primary Endpoint**

To collect and explore real-life data on the use, safety and tolerability of a systematic drug management of intravenous epoprostenol (Veletri®) treatment in patients with PAH.

Real-life safety and tolerability data will be obtained by listings of the frequency of i.v. epoprostenol (Veletri®)-associated adverse drug reactions (ADRs), serious adverse events (SAEs) and AEs during i.v. epoprostenol therapy.

